7.2.3. Subject Inclusion Criteria

1. Patients 18 years or older
2. Patients with heart failure with preserved ejection fraction (HFpEF; LVEF $\geq 50\%$)
3. Hospital admission or equivalent (such as ER visit alone or clinic visit alone) and acute decompensated HF as determined by:
 - a. Dyspnea at rest or with minimal exertion
AND
 - b. Treatment with at least one dose of IV diuretic or ultrafiltration
AND
 - c. At least two of the following signs and symptoms:
 - i. Orthopnea
 - ii. Pulmonary rales that do not clear with cough
 - iii. Congestion on chest X-ray

- iv. Local BNP or NT pro-BNP level:
 - A. No current atrial fibrillation (AFib): BNP \geq 100 pg/mL or NT pro-BNP \geq 300 pg/mL
OR
 - B. Current AFib: BNP \geq 150 pg/mL or NT pro-BNP \geq 450 pg/mL
4. Sleep disordered breathing (SDB) documented by screening polygraphy with an AHI \geq 15 events/hour (e/hr)
5. Patient is able to fully understand study information and sign informed consent

7.2.4. Subject Exclusion Criteria

1. Right-sided heart failure without left-sided failure
2. Current chronic use (within 4 weeks of study entry) of any PAP therapy (eg, CPAP, APAP, or bi-level) or contraindicated for PAP therapy
3. Sustained systolic blood pressure <80 mmHg at baseline
4. Complex congenital heart disease
5. Constrictive pericarditis
6. Chronic hypoxemia as evidenced by sustained oxygen saturation $\leq 85\%$ at rest during the day or at start of nocturnal oximetry recording or regular use of oxygen therapy (day or night)
7. Transient ischemic attack (TIA) or Stroke within 3 months prior to study entry
8. Definite clinically evident acute myocardial infarction within 3 months of study entry
9. Known amyloidosis, hypertrophic obstructive cardiomyopathy, or arteriovenous fistulas
10. Moderate or greater valvular heart disease as the primary reason for heart failure
11. Pregnant, or planning to become pregnant during the study period
12. In the opinion of the investigator, the index acute decompensated HF event was due primarily to uncontrolled AFib with fast ventricular response rate
13. Inability to comply with planned study procedures

8. STUDY DEVICES

8.1. AirCurve™ 10 ASV

The AirCurve 10 ASV (“AirCurve”) is a market-released device that has been FDA-cleared in the US (K160822) and CE-marked in Germany to provide non-invasive ventilatory support to treat patients weighing more than 66 lbs (30 kg) with OSA, central and/or mixed apnea or periodic breathing. The device is intended for home and hospital use.

AirCurve is a non-invasive device, providing minute ventilation-targeted ASV algorithms to deliver ventilatory support for OSA, CSA and/or mixed apnea, and periodic breathing by automatically adjusting the pressure support (PS) in a defined pressure range to maintain a target minute ventilation. The AirCurve 10 ASV device offers three different therapy modes, CPAP mode, ASV

mode and ASVAuto mode. The CAT-PEF Feasibility Study will only use the ASVAuto mode. Ancillary equipment includes the humidifier, air delivery hose, mask, and headgear.

In ASVAuto mode, the device automatically adjusts the expiratory pressure in order to provide only the amount of pressure (EPAP) required to maintain upper airway patency. The device analyzes the state of the patient's upper airway on a breath-by-breath basis and delivers expiratory pressure within the allowed range (Min EPAP and Max EPAP) according to the degree of obstruction. EPAP is automatically adjusted depending on three parameters: inspiratory flow limitation, snore, and obstructive apnea.

Pressure Support (PS) is defined as the difference between the peak pressure at the end of inspiration, and the minimum pressure at the end of expiration (ie, the amplitude of the pressure waveform delivered). The AirCurve pressure support (Inspiration:Expiration and Expiration:Inspiration) trigger points are set automatically based on measurement of the patient respiratory flow. The AirCurve algorithm will automatically adjust pressure delivery to keep the patient's respiratory flow even.

See AirCurve Clinician's Manual for details.

8.2. ApneaLink Air

The ApneaLink Air (“ApneaLink”) is a market-released polygraphy (“home sleep testing [HST]”) device that has been FDA-cleared (K143272) for use by Health Care Professionals, where it may aid in the diagnosis of sleep disordered breathing for adult patients. ApneaLink records the following data: patient respiratory nasal airflow, snoring, blood oxygen saturation, pulse, and respiratory effort during sleep. ApneaLink uses these recordings to produce a report that may aid in the diagnosis of sleep disordered breathing or for further clinical investigation. The ApneaLink may be used with an optional dual-lumen cannula in cases where the patient cannot be taken off low flow oxygen therapy for the duration of the test.

The ApneaLink Air recorder is a 4-channel battery-powered respiratory pressure sensor and oximetry system. The ApneaLink Air recorder and the respiratory effort sensor must be fastened with the re-usable belt on the patient's chest. All relevant respiratory information during sleep will be collected via nasal cannula, pulse oximetry adapter and respiratory effort sensor. The disposable plastic nasal cannula is connected to the ApneaLink Air recorder and fixed at the patient's nose. The oximetry sensor is connected to the patient's finger. The respiratory effort sensor is connected to the ApneaLink recorder and held in place by the belt. The physician can generate a report with the recorded and analyzed data through the web-based AirView. The default settings for the ApneaLink Air includes a flow reduction of 80% for at least 10 seconds to automatically score an apnea, a flow reduction of 30% combined with a desaturation of 3% to automatically score a hypopnea, and a respiratory effort sensor to differentiate between central, obstructive and mixed apneas.

See ApneaLink Air Clinician's Manual for details.

8.3. Device Accountability

An accurate and current accounting of the dispensing of ResMed devices (AirCurve, ApneaLink) will be maintained on an on-going basis by a qualified member of the study site using the Sponsor-provided "Device Disposition Log". Devices will be made available to the investigator by ResMed. If a replacement device is dispensed, it will be documented per device accountability procedure. All non-disposable ResMed devices must be returned to ResMed at the end of the study.

8.4. Labeling

The label contains the information as required by relevant regulatory requirements:

- a) Sponsor name and address
- b) Serial number to identify the individual device
- c) Instruction For Use

8.5. Packaging

The AirCurve 10 ASV and ApneaLink Air study devices are FDA 510(k) cleared and will be used with the standard packaging. The devices are CE marked according to the European Declaration of Conformity.

8.6. Instruction for Use

The devices will be used as specified in the relevant Instructions for Use.

8.7. Required Training

Subjects will be instructed on usage of the devices by the local Investigators or designee. ResMed will provide the investigators' training.

9. THERAPY

9.1. Treatment with Adaptive Servo-ventilation (AirCurve)

The AirCurve device will be used at home; however the therapy can be initiated in the hospital or as an outpatient within 14 days of hospital discharge. Although the AirCurve has three therapy modes, CPAP, ASV, and ASVAuto, only the ASVAuto mode will be used for this study. Subjects are advised to use the AirCurve device during any significant sleeping period, including naps. Ideally, AHI should be at or below 5 e/hr. However, if the AHI cannot be maintained below 10 e/hr, the subject's therapy should be adjusted (mask and/or pressure settings).

9.2. Set up of AirCurve in ASVAuto Mode

For initiation of therapy, AirCurve will be set to a minimum expiratory PAP (EPAP) of 4 cmH₂O, a maximum EPAP of 15 cmH₂O, a minimum pressure support of 3 cmH₂O, and a maximum pressure support of 15 cmH₂O. All subjects will be provided humidifiers and ClimateLine tubing to address

any instance of upper airway dryness or other forms of discomfort with the airflow of the device during the initiation or during therapy with the device. For the initiation of therapy, a ResMed full face mask is recommended, but if this mask is unsuitable for the subject another type of mask such as a nasal mask or nasal pillows mask will be tried. Adherence to therapy will be evaluated centrally through AirView. The recommended target for AHI within 7 days of therapy initiation is lower than 10 e/hr, and major mask leaks should be avoided. If these targets are not able to be achieved, the subject will be contacted to implement corrective actions.

The subject's AirCurve device will be added to the Trial AirView account for ongoing monitoring during the study.

9.3. AirView

AirView is the HIPAA compliant web based system that is routinely used for telemonitoring. The AirCurve device contains built in wireless connectivity which transmits data via a mobile network to a secure data center. Data is transmitted at the completion of each period of use (e.g. after each night of use). Data can then be accessed, via a login code, by the respiratory/sleep team to assess items such as device efficacy (AHI), mask leak, and usage hours.

The Adherence Core Lab will review data at least once per week for each site. Enrolling sites consistently not achieving an average of 3 hours of use per night with their subjects will be identified and contacted. The Adherence Core Lab will provide an analysis of adherence to better target potential interventions. For example, if the participant did not initiate use, the recommended intervention may be focused on remembering to put the mask on at night and promoting adherence. If the data shows that ASV was initiated but was discontinued within 1 hour, the intervention by the site may be focused on mask comfort. The study team will intervene if the subject is having issues with therapy or is struggling with compliance. See Appendix I.

AirView is compliant with HIPAA, EU 95/46/EC, and national privacy laws. Data are encrypted and all database accesses are logged and can be re-traced.

[figure not shown]
In addition to AirView, a patient-focused version of the data is available through the myAir application. The myAir application can be accessed via the subject's smartphone and allows the subject to monitor their own treatment data. The myAir application also provides tips to the subject on things like coping with therapy, managing mask leaks, and adjusting comfort settings. These tips are personalized based on each individual's data. Although the myAir App is not mandatory in this trial, subjects will be strongly recommended to use it to assist their usage of ASV. If subjects are unable to use the App they will be shown how to access equivalent information (myAir website).

10. STUDY SCHEDULE

10.1. Study Entry

A patient meets eligibility criteria of the study if all of the inclusion criteria and none of the exclusion criteria are met. Subjects will stay enrolled for the duration of the study even if they are re-hospitalized during their enrollment.

10.2. Study Flow

10.3. Follow-Up

The clinical study plan for the CAT-PEF Feasibility Study includes 1 follow up visit, which may be conducted by phone, at 3 months.

See **Section 11** for description of specific study procedures.

10.4. Screening Procedures

Patients who have been admitted to the hospital, or in the outpatient setting, if within 14 days of discharge, and have symptoms of acute decompensated heart failure will first be evaluated for eligibility for the study based on chart review.

Review the patient's records to ensure the following:

1. Evidence of HFpEF ($EF \geq 50\%$) that is not solely right-sided. HFpEF is based on most recent echocardiogram results, but must be within last 12 months.
2. This (or the most recent) hospitalization includes acute decompensated HF as determined by dyspnea and other signs and symptoms as listed in inclusion criteria.
3. The first healthcare encounter related to this hospitalization (e.g., ER, cath lab) was at least 24 hours and no more than 14 days prior to consent.

If the patient appears to be eligible based on the cardiology-related entry criteria, they may be approached about study participation. A brief interview may be conducted to further address potential eligibility criteria.

If the patient continues to appear to be eligible for participation in the study then consent will be obtained. A log of patients screened but not eligible for the study will be maintained.

NOTE: All subjects who sign a consent form must be entered in the data management system, whether or not they are entered into the study.

1. Document demographics and eligibility criteria data
2. Arrange for AHI measurement using the ApneaLink overnight. Subject is not eligible for study entry if $AHI < 15$ e/hr from ApneaLink.
3. If $AHI \geq 15$ e/hr with ApneaLink Air and other entry criteria are met, confirm tolerability of the mask and ASV therapy by having the subject use the system for a short time (awake or asleep).
4. If they are not eligible for study entry, document the reason for screen failure in the data management system.

10.5. Detailed Visit Schedule

The following visit schedule applies to subjects who met all eligibility criteria, and are enrolled in the CAT-PEF Feasibility Study.

10.5.1. Visit 1: Screening/Baseline	Primary Responsibility	
	Cardiology	Sleep
Determination of eligibility	X	
ApneaLink Test		X
Mask fitting, ASV set-up and training, myAir set-up		X
Document demographics and baseline data	X	
KCCQ-12	X	

10.5.2. ASV Adherence Monitoring	Primary Responsibility	
	Cardiology	Sleep
Follow-up with subject 2-3 days after start of therapy		X
Review AirView for adherence flags weekly		X
Contact subjects with sub-optimal adherence as needed		X
Review overall adherence at 30 days post-therapy start. Subjects not meeting adherence criteria will be discontinued from the study		X
Document contact in EDC		X

10.5.3. Visit 2: End of study Follow-up	Primary Responsibility	
	Cardiology	Sleep
Collect follow up data on death and hospitalizations	X	
Disposition AirCurve device and refer to sleep therapist		X
KCCQ-12	X	

10.6. Overview of visits

	Screening	Baseline "Day 0" (≤3 days from AL report)	2-3 days Post-device start	30 days (±2 days) "1 mo"	Weekly during study	12 weeks (±2 weeks) "3 mo"
Visit Location:	Hospital or Clinic	Hospital or Clinic	Phone call			Clinic or Phone Call
Review of HF history, signs & symptoms	X					
ApneaLink Air test	X					
ASV therapy and mask tolerance	X					
KCCQ-12	X					X
Initiation of ASV Therapy		X				
ASV Device use monitoring			X	X*	X	X

*Check to confirm adequate device use

10.7. Duration of the study

An individual subject's participation is expected to be 3 months.

With an expected enrollment period of up to 24 months for 160 evaluable subjects, and a follow-up period of 3 months, the overall study duration is calculated to be approximately 27 to 30 months.

11. VISIT PROCEDURES

11.1. Polygraphy

Every subject in the study will undergo polygraphy (including pulse oximetry) using ApneaLink at screening. Data acquisition and analysis is described in the ApneaLink Systems Clinical Guide and data collection and the settings required for automatic scoring will be described in the Manual of Procedures. Completion of the test is defined as the time the report is generated.

11.2. KCCQ-12

The short form of the Kansas City Cardiomyopathy Questionnaire is a 12-item instrument that quantifies physical function, symptoms (frequency, severity and recent change), social function, self-efficacy and knowledge, and quality of life.

11.3. Mask and ASV Therapy Tolerance

All subjects meeting eligibility criteria (AHI \geq 15 e/hr per ApneaLink) will be fitted with a mask and set up on the AirCurve. Subjects will also be entered into the AirView system, and be encouraged to use the myAir application. Preferably, subjects will use the AirCurve device and mask overnight to determine tolerance; however, if that is not possible (due to planned discharge, outpatient clinic, eg), the device and mask should be used long enough to demonstrate tolerance (awake or

asleep). Subjects who are unable to tolerate the mask or the delivered pressure will not continue with the study.

If the subject can tolerate the mask and delivered pressure, they will complete the baseline assessments and be issued an AirCurve device.

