4. PROTOCOL SUMMARY

Objectives	Demonstrate feasibility of study conduct and that acceptable adherence to ASV therapy can be achieved in recently hospitalized HFpEF patients with moderate to severe SDB.
Study Design	This study is a prospective, single-arm, unblinded, multi-center study. All subjects meeting criteria will receive adaptive servo-ventilation (ASV).
Number of Subjects	The study will aim to enroll 160 evaluable subjects. For the purposes of this study, an evaluable subject is one with ASV usage of at least 4hrs per night for 70% of the study nights, excluding nights hospitalized at 30 days after study entry. In order to achieve 160 evaluable subjects it is estimated that up to 300 subjects will be initially enrolled in the study.
Selection criteria	
Inclusion criteria for the study are:
 
 1. Patients 18 years or older 2. Patients with heart failure with preserved ejection fraction (HFpEF; LVEF $\geq 50\%$) 3. Hospital admission or equivalent (such as ER visit alone or clinic visit alone) and acute decompensated HF as determined by: 
 a. Dyspnea at rest or with minimal exertion AND b. Treatment with at least one dose of IV diuretic or ultrafiltration AND c. At least two of the following signs and symptoms: 
 i. Orthopnea ii. Pulmonary rales that do not clear with cough iii. Congestion on chest X-ray iv. Local BNP or NT pro-BNP level: 
 A. No current atrial fibrillation (AFib): BNP ≥ 100 pg/mL or NT pro-BNP ≥ 300 pg/mL OR B. Current AFib: BNP ≥ 150 pg/mL or NT pro-BNP ≥ 450 pg/mL 4. Sleep disordered breathing (SDB) documented by screening polygraphy with an AHI ≥ 15 events/hour (e/hr) 5. Patient is able to fully understand study information and sign informed consent 
Exclusion criteria for the study are:
 
 1. Right-sided heart failure without left-sided failure 2. Current chronic use (within 4 weeks of study entry) of any PAP therapy (eg, CPAP, APAP, or bi-level) or contraindicated for PAP therapy

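### Mean ASV hours will describe only eligible patients who also passed a mask and pressure tolerance test, and so overstate adherence in the wider population named by the objective

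*Combined protocol and SAP*

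**What the plan says.** **The test.** Under Section 11.3, subjects who meet eligibility are fitted with a mask, set up on the AirCurve and entered in AirView. It continues: "Subjects who are unable to tolerate the mask or the delivered pressure will not continue with the study". For the rest: "If the subject can tolerate the mask and delivered pressure, they will complete the baseline assessments and be issued an AirCurve device". Section 10.4, step 3, places the test after the AHI result and the other entry criteria: the site is to "confirm tolerability of the mask and ASV therapy by having the subject use the system for a short time (awake or asleep".

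**Eligibility.** Section 10.1 states: "A patient meets eligibility criteria of the study if all of the inclusion criteria and none of the exclusion criteria are met". Neither Section 7.2.3 nor Section 7.2.4 lists tolerance of mask or pressure.

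**Target population.** The objective in Section 4 is to show that "acceptable adherence to ASV therapy can be achieved in recently hospitalized HFpEF patients with moderate to severe SDB". The study design entry in the same section says that every subject who meets criteria gets ASV.

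**Analysis.** Section 13.2 estimates mean usage with a 95% interval and names no analysis set. Sections 7.2.2 and 13.1 tie endpoint evaluation and sample size to 160 evaluable subjects, meaning those who reach 4 h on 70% of days by day 30. Section 11.5 discontinues the others.

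**Test length.** Section 11.3: "Preferably, subjects will use the AirCurve device and mask overnight to determine tolerance". Where planned discharge or a clinic setting rules that out, "the device and mask should be used long enough to demonstrate tolerance". Section 10.4 does not mention an overnight test. Neither section gives a minimum time or a pass rule.

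**The concern.** A patient who meets every listed criterion but cannot bear the mask or the pressure belongs to the population in the objective. Such a patient goes home without a device and has about zero hours of home use. Leaving these patients out raises the mean relative to that population.

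This matters because of what the study is for. Section 5.1 says that very low adherence limited the preceding trial, and that this study should support a phase III randomised trial. A planner who reads the mean as the adherence to expect among eligible patients would expect too much, unless the later trial applied the same test and counted patients only after it.

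The test also acts before a device is issued. Widening the analysis from evaluable subjects to everyone who started ASV at home would deal with the day-30 rule and leave this earlier filter in place.

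**Working it through.** **1. The plan's own figures (Section 13.1).** SD 1.6 h, n = 160, 95% confidence.

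- Half-width = 1.96 × 1.6 / √160 = 0.248 h (0.2498 h with the t quantile). The stated 0.25 h or less is reproduced.
- Enrolment = 160 / 0.60 = 266.7, against the stated 266. The difference is rounding.
- Neither figure allows for losses at the tolerance test. The text does not say whether tolerance failures count among the up to 300 enrolled or within the 40% not evaluable.

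**2. Effect on a mean over everyone issued a device.** Let f be the share of eligible tested subjects who fail, and M the mean hours among those issued a device. Failures count as 0 h.

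- Mean over all eligible = (1 − f) × M
- Overstatement = M − (1 − f) × M = f × M

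The documents give neither f nor M, so both are assumed over a range. Overstatement in hours per day:

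| f | M = 3 | M = 4 | M = 5 | M = 6 |
|---|---|---|---|---|
| 2% | 0.06 | 0.08 | 0.10 | 0.12 |
| 5% | 0.15 | 0.20 | 0.25 | 0.30 |
| 10% | 0.30 | 0.40 | 0.50 | 0.60 |
| 20% | 0.60 | 0.80 | 1.00 | 1.20 |

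**3. Effect on the evaluable share.** With 60% of issued subjects evaluable, the share among all eligible tested subjects is 0.60 × (1 − f): 57% at f = 5%, 54% at 10%, 48% at 20%.

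**4. The two filters together.** To be evaluable, a subject needs at least 0.70 × 4 = 2.8 h per day on average over the first 30 days, hospital days excluded. Someone who cannot tolerate the mask or pressure would seldom reach that. Illustration with assumed means of 6 h (evaluable) and 2 h (issued but not evaluable), and f = 10%:

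- Evaluable mean: 6.00 h
- All issued: 0.60 × 6 + 0.40 × 2 = 4.40 h
- All eligible: 0.90 × 4.40 = 3.96 h
- Gap: 6.00 − 3.96 = 2.04 h, of which the day-30 rule accounts for 6.00 − 4.40 = 1.60 h and the tolerance test for 4.40 − 3.96 = 0.44 h

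On these assumptions the day-30 rule is the larger source. The test's own share appears only once the mean is taken over everyone issued a device.

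**The case against.** The strongest objection is that the planned mean is over evaluable subjects, and the day-30 rule would exclude most intolerant subjects anyway. Dropping the tolerance test would hardly move that mean. This stands. A reader might infer that the test by itself materially biases the planned primary mean, and the documents do not support that.

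A reader might also set the overstatement against the 0.25 h margin and conclude that about 6% failing is enough to exceed it. That threshold is 0.25 / 4.0 = 6.25% and rests on an assumed mean of 4 h; for means of 3 to 6 h it runs from 8.3% down to 4.2%. The margin also belongs to the 160 evaluable subjects, not to everyone issued a device.

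Three further inferences go beyond the text:

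- **Inpatients get the overnight test and outpatients the short one.** Section 11.3 prefers overnight use for all subjects, and its planned-discharge exception covers inpatients. The short-time wording is Section 10.4's, for everyone. Unequal length could make selection uneven, but does not itself create the overstatement.
- **A planned adherence comparison by place of recruitment is confounded.** Neither Section 4 nor Section 13 plans one.
- **Failures have no usage record at all.** They are entered in AirView around the test, so a brief record may exist. What they lack is home use.

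It is also fair to say that a tolerance check is a legitimate screening step. Section 10.6 schedules it under screening, consented subjects are entered in the data system, and reasons for screen failure are a secondary endpoint. But Section 10.4, step 4, ties that record to ineligible subjects, while Section 11.3 treats these subjects as eligible, so their classification is unclear. Exclusion 13, on inability to comply with procedures, could be stretched to cover them, but does not mention tolerance. On either reading they remain outside the mean.

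**Conclusion.** The point holds in limited form. Mean hours will describe patients who passed a tolerance test that is not part of the stated eligibility, and will overstate adherence in the population the objective names. The direction follows from counting a patient without a device as having zero hours of home use. It does not assert what such a patient might have used if issued a device.

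The size cannot be found from the documents. It is f × M, or 0.06 to 0.12 h at 2% failing and 0.30 to 0.60 h at 10%, for assumed means of 3 to 6 h among those issued a device. The added effect on the planned evaluable mean is small. The test and the day-30 rule push the same way and need one joint treatment. This is a matter of reporting and of describing the population, not a reason to remove the test.

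**What to change.** - **Section 13.2.** Beside the planned mean, report mean hours (a) among all subjects issued a device and (b) among all consented subjects who met the entry criteria, with tolerance failures at zero hours. Since Section 11.5 discontinues subjects at day 30, state how their remaining nights count in (a) and (b). If these figures are not added, limit the conclusion, and the objective in Section 4, to patients who passed the test.
- **Section 10.4, step 4.** Record tolerance failure as its own reason, with the setting and the length of the test, and tabulate it. State whether these subjects count as screen failures or as enrolled.
- **Sections 10.4 and 11.3.** Reconcile the two descriptions of test length. Which length is right is for the clinical team.

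The cost is protocol wording, two eCRF fields and a less favourable adherence figure beside the planned one. Section 10.4 already has every consented subject entered in the data system, so no new population has to be followed and the test itself stays.
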